3. To investigate the criterion validity of the combination of thigh and ankle accelerometer inclinometer outputs to correctly determine the sitting position. This

will determine whether an algorithm can be constructed using the two inclinometer readings, which will better distinguish the sitting from the standing position.

4. To evaluate, from a user perspective, the acceptability of these devices in relation to the placement sites used. This will be achieved by asking patients to score the answer to a particular question through the use of a Likert scale. The question is:
 - How would you rate the comfort of wearing the accelerometers?

In consideration of the results from the feasibility study undertaken by the CI and research using the addition of a thigh mounted accelerometer to identify the sitting position (Skotte et al., 2014), the following hypotheses can be constructed:

Hypotheses

1. An ankle mounted Actigraph GT3X accelerometer, will accurately identify both the lying and standing positions when compared with direct observation as a criterion measure.
2. An ankle mounted Actigraph GT3X accelerometer, will capture a step count comparable to that recorded by direct observation in a population resident on a hospital ward recovering from critical illness.
3. The combination of inclinometer outputs of both the thigh and ankle placement sites will permit development of an algorithm permitting the ability to better distinguish between the sitting and standing position.
4. The ankle and mid-thigh accelerometer placement sites will be well tolerated by patients recovering on a ward from critical illness.

Subject selection and involvement

The study will invite adult hospital ward patients recovering from critical illness to wear one Actigraph GT3X accelerometer on the antero-medial mid-thigh and another on the ankle, resting above the lateral malleolus of the same leg. The accelerometers will be worn for a period of time not exceeding three hours. Each device will be attached with a single patient use broad elastic belt, secured by Velcro fastening, using a standardised placement protocol. The non – dominant leg will be the preferred placement side.

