Participants will be asked to undertake a semi - structured movement protocol, consisting of low intensity movements typical of those that they will already be taking through the day. These include lying in bed, getting out of bed to sit over the side, moving from sitting to standing, sitting in a chair and walking distances that their current level of physical ability permits. The observation period will be undertaken at a time mutually agreed between the participant and the observer (the CI). Observation periods will not occur over lunchtimes or protected patient rest periods, which vary from ward to ward. Rest periods will be encouraged if required and should the participant request them.

Participants will determine the order in which they perform the movements, but as many as possible must be completed within a period not exceeding three hours. It is envisaged this will reduce bias due to order effects and enable the determination of accelerometer validity in as naturalistic conditions as possible, whilst also permitting participant autonomy.

Inclusion Criteria

- 18 years of age or above.
- Ventilated in excess of 48 hours during admission in the ICU
- Currently resident on a hospital ward (secondary care) following step down from ICU
- At a stage in recovery where individuals are able to undertake all postural transfers independently or with minimal assistance (one person only)
- Able to mobilise short distances, either independently or with assistance from a walking aid or one person
- Willing to permit application of two Actigraph GT3X accelerometer devices, one lying anteromedially around the non-dominant mid-thigh; the other resting above the lateral malleolus on the same (ipsilateral) leg. Each device weighs 27g with dimensions of 3.8cm x 3.7cm x 1.8cm.
- Participants must be willing to consent to a period of direct observation for a length of time not exceeding three hours, which will take place at a mutually agreed time. Observation will serve as the criterion measure which accelerometer data will be compared against.

Exclusion Criteria

- Unable to provide informed written consent, or unwilling to consent to a period of observation not exceeding three hours.
- Those unable to make an informed decision about participation or demonstrating an inability to interpret information or follow study instructions as a result of impaired cognitive function.

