Following completion of the data collection period, the information captured by the accelerometers will be downloaded as soon as possible onto the laptop computer. The time when a movement commenced and ceased (with the addition of five seconds to accommodate accelerometer processing), will be noted by the CI. The type of movement and body positions adopted will also be documented (lying, sitting or standing). If the movement involves walking, the CI will count the number of steps undertaken manually, entering all of the above information onto a data collection sheet. The participant will not miss any refreshments, food or any investigations and they will also be encouraged to undertake usual daily activities, e.g. reading a paper or watching the television. If the participant requests some time alone, in the case of making a phone call for example, the CI will comply, but encourage the participant to remain in the same body position. If they were sitting in a chair for example, they would be encouraged to remain seated, agreeing a time for the CI to return (e.g. fifteen minutes). Should any procedures or personal cares be necessary, the CI will respect the need for privacy and dignity and leave until they are complete. The data captured by the accelerometers during these time periods will be excluded from data analysis, as there will be no criterion measure (observation) to compare accelerometer data against.

Observational data will be collected by the CI using a data collection form specifically designed for this purpose, which will be entered into an electronic format within the IBM SPSS statistics programme (version 20) for data analysis. The CI will undertake all data collection procedures and undertake statistical analysis.

Upon completion of the period of observation the accelerometers will be removed and the skin examined for one final time. Participants will be asked to rate their views on acceptability of wearing the accelerometers at the two placement sites. They will be asked to consider the question in relation to the individual placement sites and in combination. One question will be asked:

1. How would you rate the comfort of wearing the accelerometers?

[figure not shown]
Participants will be requested to match their answer to a statement on a five-point Likert Scale which will be printed on a sheet for them:

1. Very uncomfortable
2. Somewhat uncomfortable
3. Neither comfortable or uncomfortable
4. Somewhat comfortable

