5. Very comfortable

A similar method of gaining feedback from participants regarding accelerometer comfort has been used in previous studies (Kramer et al., 2013).

Participants will also be asked if they have any comments they wish to make regarding the accelerometers, which will be noted as free text should any be forthcoming.

Study format

Semi structured movement protocol

1. Lying in bed with the legs straight and the bed head set at a comfortable height as dictated by the participant
2. Lying on the left side
3. Lying on the right side
4. Moving from lying to sitting over the side of the bed
5. Sitting to standing
6. Sitting in a chair
7. Mobilising a distance determined by the functional ability of the individual participant at that point in their recovery.

N.B. The participant will be free to undertake these movements in any order they wish, but there is a requirement to undertake as many of these movements as possible within the observation period, which will not exceed three hours. The participant will be provided with a sheet to remind them of the movements required to be undertaken. This will contain a tick box so they can mark off when a particular movement was completed. If a movement is missed, the CI will encourage the participant towards the end of the observation period to undertake it.

Infection control considerations

Advice has been sought from the HEYHT Infection Control Team regarding infection control considerations when using the accelerometers with patients' resident within HEYHT. The recommendations are as follows:

1. Elastics belts must be single patient use only and fastened using Velcro
2. The part of the accelerometer that permits download to the computer should be covered with a piece of easily removable tape (e.g. 'Scotchtape') to permit the whole device to be swabbed down with a Tristel wipe following the three-hour period of data collection per participant.
3. The devices are not required to be placed in a nylon pouch prior to application.

Tissue viability considerations

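### Two hypotheses concern standing, but no movement task asks the participant to stand still and no rule says whether walking counts as standing, so the standing result may rest on a few static seconds or mainly describe walking.

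*Combined protocol and SAP*

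**What the plan says.** Under Hypotheses, Hypothesis 1 is that the ankle device "will accurately identify both the lying and standing positions when compared with direct observation as a criterion measure". Hypothesis 3 is that combining thigh and ankle readings will give an algorithm "permitting the ability to better distinguish between the sitting and standing position".

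The tasks are described twice. Subject selection and involvement says "These include lying in bed, getting out of bed to sit over the side, moving from sitting to standing, sitting in a chair", and then adds walking as far as ability allows. The numbered list under Study format gives lying three posture items, starting with "1. Lying in bed with the legs straight and the bed head set at a comfortable height" and continuing with each side. Sitting has one posture item, "6. Sitting in a chair", and is also the end of a transfer in item 4. Standing has "5. Sitting to standing", which is a transfer, and whatever item 7 supplies: "Mobilising a distance determined by the functional ability of the individual participant at that point in their recovery". No item has a duration or a number of repeats. Participants are to complete as many items as they can, in any order, within a three-hour cap.

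Study procedure sets one-second epochs. It has the observer let five seconds pass after a postural change before recording the new position, to allow for the way the device processes data. During the session, "they will also be encouraged to undertake usual daily activities, e.g. reading a paper or watching the television". The observer records position as lying, sitting or standing. Data collection process lists four inclinometer readings (off, standing, lying, sitting), none of them for walking.

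Statistical analysis plans kappa across the positions and percentage agreement for each position, by placement site.

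**The concern.** Standing is a target posture in Hypothesis 1 and the comparator in Hypothesis 3, yet the protocol does not ensure that any static standing is observed. A participant who rises and walks off at once has completed items 5 and 7.

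Two consequences follow. First, if walking seconds are not counted as standing, the standing analysis may rest on a few seconds per person. It could have none if the five-second wait is dropped from analysis, and the plan does not say whether it is. Second, if walking seconds are counted as standing, the standing percentage may largely measure how the inclinometer reads a walking leg. The question of whether it can tell a still, upright patient from a seated one would then be barely tested. That question matters for a device meant to separate activity from inactivity on a ward. Standing data not collected during the session cannot be recovered at analysis.

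**Working it through.** **Plan's own figures.** The plan gives no figure for standing time. Its only computed figure is the cited 12 subjects for r = 0.75, alpha 0.05, power 0.9. By Fisher z, one-sided, n = ((1.645 + 1.282)/0.973)² + 3 = 12.05; two-sided it is 14.1. The figure is broadly reproducible, but it concerns a correlation and says nothing about standing.

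**Step 1. Percentage agreement when walking is pooled with standing.** Assume 10 s of static standing, all misread, and w seconds of walking, all read as standing. Agreement for standing = w/(w + 10):

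- w = 30: 30/40 = 75%
- w = 60: 60/70 = 86%
- w = 120: 120/130 = 92%
- w = 300: 300/310 = 97%

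Agreement on static standing is 0% in every row.

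**Step 2. Overall kappa.** Assume a session of N one-second epochs with S seconds of standing. The rest is split equally between lying and sitting, each read correctly 90% of the time, with errors going to the other of the two. Kappa = (p_o − p_e)/(1 − p_e). For N = 10,800 (the three-hour cap) and S = 60, lying and sitting have 5,370 s each.

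- Standing all correct: p_o = (0.9 × 10,740 + 60)/10,800 = 0.9006; p_e = (5,370² + 5,370² + 60²)/10,800² = 0.4945; kappa = 0.4061/0.5055 = 0.803.
- Standing all read as sitting: p_o = 9,666/10,800 = 0.8950; p_e = (5,370 × 5,370 + 5,370 × 5,430)/10,800² = 0.4972; kappa = 0.3978/0.5028 = 0.791.

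The same calculation for other values:

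| Session | Standing time | Kappa, standing all right | Kappa, standing all wrong |
|---|---|---|---|
| 3 h | 10 s | 0.801 | 0.799 |
| 3 h | 60 s | 0.803 | 0.791 |
| 3 h | 300 s | 0.815 | 0.757 |
| 3 h | 1,200 s | 0.850 | 0.640 |
| 1 h | 60 s | 0.810 | 0.774 |
| 1 h | 300 s | 0.840 | 0.677 |

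The 90% accuracy is not critical at short standing times. With 60 s in three hours and lying and sitting read perfectly, kappa is 1.000 against 0.989. With lying perfect and 30% of sitting read as standing, it is 0.742 against 0.731.

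For the 92% example in Step 1, placed in the three-hour session with the Step 2 assumptions, p_o = (0.9 × 10,670 + 120)/10,800 = 0.9003 and p_e = 0.4886, so kappa = 0.805.

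**Step 3. Precision if walking is excluded.** Assume 20 participants, 10 s of static standing each, true agreement 90%, and within-person correlation ICC. Effective n = 200/(1 + 9 × ICC). For ICC 0.2, 0.5 and 0.8 this is 71, 36 and 24, with 95% Wilson intervals of 81–95%, 76–96% and 72–97%.

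Session length, time split, accuracies, seconds of standing and walking, and ICC are all assumptions. The epoch length, the three-hour cap and the 20 participants come from the protocol.

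**The case against.** The strongest reply is that the plan does not rely on kappa. It also gives percentage agreement for each position, which is the natural test of Hypothesis 1. If all standing were misread, that percentage would be 0% however short the standing. This is right, and it limits the kappa argument. A reader might infer that the study could support Hypothesis 1 for a device that never recognises static standing. The documents do not support that in general; it could happen only if walking seconds are pooled into standing, and the plan leaves this open.

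A second reply is that walking is upright and has no code of its own, so it may be intended to count as standing; item 7 would then supply ample data. That is plausible but unstated, and it is the situation in which the 92% arises.

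Third, the feasibility study used similar movements and reported that the ankle site identified standing well. This shows that such tasks can yield standing data. It was, however, done in healthy volunteers simulating weakness, and the protocol does not say how much of that standing was static.

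Fourth, three hours is a cap and unobserved time is excluded, so dilution may be less than in the three-hour rows; the one-hour rows show this.

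Fifth, the loose structure is deliberate, to keep conditions naturalistic. That argues against timing every posture. It does not argue against one short stand, since the protocol already scripts side lying and prompts for missed items.

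**Conclusion.** The gap is real and worth fixing before sessions start. There is no held standing item and no rule on walking seconds, so static standing may rest on a few seconds per person and the standing percentage may mainly describe walking. Under the stated assumptions that percentage can reach 92% with no static standing recognised, and overall kappa moves by only about 0.01 when 60 s of standing in three hours goes from all right to all wrong.

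Four stronger readings do not hold:

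- Standing data need not be scarce. Patients may stand longer of their own accord, and the observer would record it; the protocol simply does not secure it.
- It is not the case that no time at all is attached to a posture. The five-second wait exists, although it is not a hold.
- Sitting does not have two posture items against none for standing. Item 4 is a transfer just as item 5 is, so sitting has one.
- The lying and sitting tasks do not need minimum times. Both already have posture items, and the session encourages sedentary activity.

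**What to change.** 1. In the Study format list and the participant's tick sheet, extend item 5 so that rising is followed by a brief period of standing still, if able. The investigator should set the duration and any repeats, within the existing three-hour cap.
2. In Statistical analysis, state how walking seconds are coded. Report percentage agreement for static standing separately from walking, with the seconds of each per participant.
3. State whether the five seconds after a postural change are analysed, excluded or assigned to the previous position.
4. Leave the lying and sitting items untimed.

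The cost is one line in the list and tick sheet, a few sentences in the analysis section and a little time within the session, with no extra staff. The downside is a slightly more scripted session.

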Body mass index (BMI) will be calculated by using the latest weight recording (in kilogrammes) on the participants observation charts and asking participants to estimate their height, which will be converted to centimetres if given in feet and inches. Participants will wear two Actigraph GT3X accelerometers, one anteromedially around the mid - thigh and the other around the ankle of the same (ipsilateral) leg resting above the lateral malleolus. The CI will attach the accelerometers, ensuring they feel comfortable and pose no circulatory concerns. The placement sites will be checked on a half hourly basis during the data collection period. This has been recommended by the tissue viability team, to ensure the accelerometers are not compromising skin integrity or circulation. A standardised assessment form will be used for this process, which has been constructed with assistance from the tissue viability team.

The data collection period will not exceed three hours; including rest periods. Accelerometers will be removed at any time during the data collection period should a participant request this. Any data that has been collected during the time period that the accelerometers were worn prior to the request for removal will be downloaded and included within the analysis with the participant's permission.

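### The comfort rating behind hypothesis 4 is collected by the investigator who fits the devices, with no private return described, so the share answering comfortable is at risk of courtesy bias; early removers may also go unrated

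*Combined protocol and SAP*

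**What the plan says.** Objective 4 (under Defining the research question) asks how acceptable the devices are to users, by way of one Likert question on comfort. Hypothesis 4 states that both placement sites will be well tolerated.

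One person holds every role around that question. Under Recruitment of study participants, the chief investigator explains the study, obtains consent and countersigns the form. Under Study procedure:

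- Fitting: "The CI will attach the accelerometers, ensuring they feel comfortable and pose no circulatory concerns".
- Observation is by the chief investigator, for a period of at most three hours.
- Collection and analysis: "The CI will undertake all data collection procedures and undertake statistical analysis".
- Timing: "Upon completion of the period of observation the accelerometers will be removed and the skin examined for one final time", and the comfort question follows: "Participants will be asked to rate their views on acceptability of wearing the accelerometers at the two placement sites".
- Response: "Participants will be requested to match their answer to a statement on a five-point Likert Scale which will be printed on a sheet for them". The question is put for each site and for the two together. Any comments are noted as free text.
- Early removal: "Accelerometers will be removed at any time during the data collection period should a participant request this". Data captured up to that point are kept with permission. Nothing is said about a comfort rating in that case.

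Under Statistical analysis, the five answers are collapsed to three groups: the two comfortable answers, the neutral answer on its own, and the two uncomfortable answers. They are reported as percentages, with no test or threshold.

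**The concern.** A participant who has just spent a session with the person who recruited them, fitted the devices and took care that they were comfortable may prefer not to tell that person that they were uncomfortable. The study also belongs to that person's PhD, as the protocol states. Such a courtesy effect would run one way, towards comfortable answers, and nothing in the plan works against it.

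Early removal raises a second question. People who ask for the devices to come off may include those who disliked them most. If they are not asked, the percentages describe only those who stayed to the end.

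At stake is the reading of hypothesis 4. The comfort percentages are its only planned numerical evidence; free-text comments are the other source.

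**Working it through.** The plan gives no expected comfort percentage, so there is no figure to reproduce. The only sample-size calculation it quotes, 12 subjects for a correlation of 0.75, comes from another study and has no bearing here. The steps below show how far the percentages could move under stated assumptions.

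**Inputs from the plan.** n = 20 (Sample size calculation); five answers collapsed to three groups (Statistical analysis).

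**Step 1: weight of one participant.** 1/20 = 5 percentage points.

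**Step 2: which changes count.** Only an answer that moves from the neutral or uncomfortable groups into the two comfortable answers raises the comfortable share. A move from very to somewhat uncomfortable, or from somewhat to very comfortable, changes no reported percentage. A move from uncomfortable to neutral leaves the comfortable share alone but lowers the uncomfortable share by 5 points.

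**Step 3: a simple shift model (assumption).** Let p be the true comfortable share and q the fraction of the remaining participants who answer comfortable out of courtesy. The expected reported share is p + (1 − p) × q.

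| True share p | q = 0.10 | q = 0.25 | q = 0.50 |
|---|---|---|---|
| 60% (12 of 20) | 64% | 70% | 80% |
| 80% (16 of 20) | 82% | 85% | 90% |

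For example, 0.60 + 0.40 × 0.25 = 0.70, which is 2 of the 8 not-comfortable participants crossing. Neither p nor q is in the documents.

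**Step 4: comparison with sampling error.** Exact (Clopper-Pearson) 95% intervals at n = 20:

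- 14/20 = 70%: 45.7% to 88.1%
- 16/20 = 80%: 56.3% to 94.3%
- 18/20 = 90%: 68.3% to 98.8%

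Shifts of the size in Step 3 lie inside these intervals, so the data could not reveal them.

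**Step 5: how strong an assumption a large shift needs.** Going from 14/20 to 18/20 is 20 points. It requires 4 of the 6 not-comfortable participants to cross: 4/6 = 67%.

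**Step 6: early removers (assumption).** Suppose 16 of 20 are truly comfortable and 2 participants who stop early are not rated.

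- If both were not comfortable: 16/18 = 88.9% is reported in place of 80%.
- If both were comfortable: 14/18 = 77.8% is reported in place of 80%.

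The error is favourable only if those who stop early are less comfortable than the rest. That is plausible, but the documents do not establish it.

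**The case against.** The strongest reply is that the risk is inferred. The plan has participants match an answer on a printed sheet and does not say how the answer is returned, so a face-to-face reply follows only from the statement that the chief investigator does all data collection. The investigator is not constantly at the bedside either: distance follows the participant's wishes, and the investigator leaves for personal care or on request. Comfort is a descriptive aim with no threshold. All of this stands, and it is why the point is a risk and not a demonstrated bias. It does not remove the risk, because the plan describes neither a private return nor a second collector.

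A reader might also infer that the inclusion criterion "Willing to permit application of two Actigraph GT3X accelerometer devices" tilts the ratings. The documents do not support that. Willingness before wear is inherent in any consented wear study, and people who decline have no comfort experience to report. The criterion limits how far the result generalises; it does not distort the answers of those who wear the devices. The plan describes no log of refusals or reasons, but that is a reporting gap.

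On early removal, it can be said that observation is complete once the devices come off, so the rating would follow as usual. The text allows that reading but does not state it.

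**Conclusion.** The point holds as a risk of courtesy bias in the favourable direction, arising because one investigator consents, fits, observes, collects and analyses, with no private return described. The size of the bias is unknown. What can be said is that each participant who crosses into a comfortable category adds 5 points at n = 20. It would be tempting to quote a rise of 10 to 20 points, but that needs 2 to 4 participants actually to cross, and softening an answer within the scale often does not do so.

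The unstated handling of early removers is a separate gap. Its effect depends on how many there are and how they would have answered.

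The consequence is confined to objective 4 and hypothesis 4. The kappa, percentage agreement and Bland-Altman analyses do not use the ratings. This is worth correcting because it is cheap, not because it threatens the study's main results.

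**What to change.** Amend the Study procedure section in two places.

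1. After the final skin check, the participant marks the printed five-point scale for thigh, ankle and both together, in private, and seals it in an envelope bearing only the study number. The envelope is opened at data entry.
2. The same rating is obtained from anyone who asks for early removal, and the report states how many of the ratings come from early removers.

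The cost is envelopes and a sentence or two of text, with no extra staff. It is practicable for these patients: they must be able to sign the consent form themselves, and they are already given a tick-box sheet for the movements.

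There are two small downsides. Free-text comments may be shorter when not prompted. The rating is private when given but not anonymous, since under Data handling and confidentiality the chief investigator can link study numbers to participants; the envelope eases the pressure at the moment of answering and does no more than that.

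A tally of patients approached and declining, and exact intervals beside the percentages, would be useful reporting additions. They describe generalisability and precision, and neither reduces courtesy bias.
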